Naloxone, one of the drugs you will receive, is commonly used to reverse the effects of opiates. It has not been shown to produce tolerance or dependence. Most of the associated risks are related to the withdrawal symptoms experienced by those with an opioid dependence. The most common risks reported post-operation are nausea and vomiting, reversal of pain relief, agitation, and changes in blood pressure. However, in studies similar to ours, the only reported side effects are dry mouth and dizziness.

Your urine will be tested for illegal drugs before each study session. If your drug test is positive, you will not be included in the present study. The results of the drug testing will be noted in your NIH medical record. If you do not want this information in your medical record, you should not participate in this study. In addition to this drug screening, participants who are able to become pregnant will have a pregnancy test. If positive, you will not be able to participate because it is unknown if MRI scanning is safe for a developing fetus. We will also document the date of onset of your recent menstrual cycle.

Do you have any questions for me about the study? Are you still interested in participating?

YES NO

IF YES: Before I schedule you for a screening visit, I will ask questions to verify that you are eligible to participate. Please answer honestly so that we can determine whether it is safe to include you in our study. You don't have to answer questions that you do not feel comfortable answering. All information you provide will remain confidential and, if for some reason you cannot participate, all the information collected will be destroyed.

Subject's Information:

1. Last name: _____ First name: _____

2. Address: _____ City: _____ Zip: _____
 3. Best Tel: _____ Email: _____
 4. DOB (mm/dd/yyyy): ____ / ____ / ____
 5. Weight _____ (lbs) height: _____
 5. Sex: M F

VERIFYING INCLUSION CRITERIA

CRITERIA	ANSWER	INCLUDE IF
Can you read and speak English easily (fluent in English)?	 YES  NO	YES
What is your age?		18≤ or ≤50
Are you able to provide written informed consent?	 YES  NO	YES
Administer Edinburgh Handedness Inventory [53]. Right-handed?	Right  Left 	Right

VERIFYING EXCLUSION CRITERIA

CRITERIA	ANSWER	EXCLUDE IF
Weight 551 lbs or higher?	 YES  NO	YES
Do you have a congenital limb deficiency or amputation of a leg?	 YES  NO	YES
Have you used recreational drugs in the past month (e.g., marijuana, MDMA [“ecstasy” or “molly”], LSD, cocaine, methamphetamine, heroin, prescription and/or opioids)?	 YES  NO	YES
Are you pregnant or breastfeeding?	 YES  NO	YES
Are you able to comply with the study procedures and visits? This includes the ability to schedule a second session within 14 days of the first session.	 YES  NO	NO
Have you had any dermatological conditions (such as a scar, burn, or tattoo) in the testing region in the last four weeks that might influence the sensitivity of your skin? Any known nerve damage? Any skin area with numbness, prickling/tingling, changed sensitivity to touch or temperature, decreased sense of vibration?	 YES  NO	YES
Do you currently suffer from chronic pain or have you suffered from chronic pain in the past year (pain lasting more than 6 months) or do you have ongoing treatment with medications for neuropathic pain (e.g. gabapentin, tricyclic antidepressants, pregabalin, tramadol)?	 YES  NO	YES
You must be able to lie comfortably flat on your back for up to 75 minutes in the MRI scanner. Do you have claustrophobia or are you uncomfortable in small closed spaces?	 YES  NO	YES
Do you have a chronic systemic disease (e.g. diabetes)?	 YES  NO	YES

Have you ever been diagnosed with major depression, an anxiety disorder, substance or alcohol dependence or abuse, post-traumatic stress syndrome, bipolar disorder, psychosis, attention-deficit/hyperactivity disorder or attempted suicide? Or do you have ongoing treatment with medications for any of the above (e.g. Selective serotonin reuptake inhibitors (SSRIs), Serotonin and norepinephrine reuptake inhibitors (SNRIs), Tricyclic antidepressants (TCA), Monoamine oxidase inhibitors (MAOs), Benzodiazepines, Anti-epileptic drugs (AEDs), Hydroxyzine (antihistamine), Antipsychotics, Disulfiram, Varenicline, central stimulants such as Methylphenidate).	 YES  NO	YES (if current/lifetime according to MINI)
Do you have a major medical condition such as kidney, liver, pulmonary, autonomic, cardiovascular (e.g. blood clots, hypertension, preexisting cardiac arrhythmia), or neurological disease (e.g., seizure disorder)?	 YES  NO Circle which one	YES
Do you currently, or have you ever, had blood clots in your leg?	 YES  NO	Yes
Do you have any metal in your body that would make having an MRI scan unsafe? This includes pacemakers, medication pumps, aneurysm clips, shrapnel fragments, permanent eye liner, or small metal fragments in the eye that other metal workers may have.	 YES  NO	YES
How many alcoholic beverages do you consume each week? A "standard" drink according to the NIAAA website http://rethinkingdrinking.niaaa.nih.gov/whatcountsdrink/whatsa_stdarddrink.asp is any drink that contains about 0.6 fluid ounces or 14 grams of "pure" alcohol. This corresponds to: 12 fl oz regular beer (5%) 8-9 fl oz malt beverage (7%) 5 fl oz wine (12%) 3-4 fl oz fortified wine such as sherry, port (17%) 2-3 fl oz cordial liquor or aperitif (24%) 1.5 fl oz brandy (40%) 1.5 fl oz shot or 80-proof spirit (hard liquor) (40%)	Regular beer: Strong beer: Wine: Fortified wine: Cordial Liquor: Brandy-like: Shots/hard liquor:	Women: > 7 Men: > 14
Are you an NIH employee who is subordinate, a relative, or co-worker of any of the investigators, or are you an NCCIH DIR employee?	 YES  NO	YES
Do you have allergies to naloxone or similar drugs?	 YES  NO	YES
Do you use any medications that may affect opioid pathways (e.g. loperamide or dextromethorphan), could potentially interact with naloxone (naltrexone, methylnaltrexone, droperidol, fenfluramine and clonidine)	 YES  NO	YES
Do you use any herbal preparations (such as yohimbine)?	 YES  NO	YES

EVALUATION OF MEDICATION USE

Have you taken any medication in the last 30 days other than over-the-counter NSAIDs or acetaminophen, including OTC, RX, topical pain-relieving creams?

Medication / Treatment	Indication	Dosage/ Interval	Start Date	End Date	Comments

If unclear: Thank you. I'll discuss this information with my team to make sure you're a good match for our study and I'll contact you soon.

Date of follow up call: (mm/dd/yyyy): ____ / ____ / ____ ; Time: ____ AM/PM

If not eligible: Unfortunately, it doesn't look like this study is a good match for you. I am going to shred the information you gave me. If you'd like to find other studies that might be a better match, you can get in touch with the clinical recruiting office or go online to Clinicaltrials.gov (*If exclude, log and shred*)

If eligible: It looks like you would be a good match for our study. I'd like to go ahead and schedule you for your first visit.

If they're new add: "You will need to go through a separate admissions process with the NIH before you begin your visit with us and that can take anywhere between 15 minutes and an hour depending on how many other people are there that day."

	Discussed communication for scheduling.	Prefers (circle one): Phone Email
	Would you like me to send you: the consent form, map/directions, appointment confirmation?	
	Discussed compensation	
 Study session (Sensory testing with MRI): \$150 each, \$300 total for study
	Explained transportation	Transportation will not be reimbursed but free parking is available (validation).
	Updated enrollment log and assigned subject code	

SCHEDULE SESSION 1 ____ ; Time: ____

REMINDER: *If you consume alcohol or use pain medications or pain-relieving creams on the testing area in the 24 hours prior to your session, we will need to reschedule your session. We will email or call you the day before your appointment. Please contact me if you have any questions between now and your appointment*

In-Person Screening Form

Subject ID: _____

Date _____

Session 1

If participant answers YES to one or more questions below, they will be rescheduled up to two times rather than excluded (participants with positive pregnancy tests will be excluded, however). If the participant is found non-compliant, i.e., answered YES to one or more questions below, during the second rescheduled appointment, he or she will be excluded from the study. All eligibility criteria will also be reviewed and confirmed by a LHP.

CRITERIA	ANSWER	RESCHEDULE EXCLUDE IF
Drug test (tox screen)	 POS  NEG	POS
Pregnancy test (those able to become pregnant)	 POS  NEG	YES
In the last 24 hours, have you consumed alcohol?	 YES  NO	YES
Is the participant showing behavioral signs of intoxication? 
Speech: overly talkative, argumentative, opinionated or interrupting; stumbling over words; loud, inappropriate language or jokesCoordination: slowed or delayed reactions, stagger, swagger, or swayAppearance: vacant or blank expression, smell of alcohol on breath, untidy appearanceBehavior: overly friendly or withdrawn, inappropriate or risky actions, attention difficulties	 YES  NO	YES
Is the participant showing signs of alcohol withdrawal syndrome (e.g. symptoms of hand tremors, irregular heart rate, fever, nausea, sweating, dehydration, headache, or confusion)?	 YES  NO	YES
In the last 24 hours, have you used a topical pain-relieving cream (e.g. methylsalicylate, capsaicin) on your arms?	 YES  NO	YES
In the last 3 days, have you used any non-steroidal anti-inflammatory drug (NSAID) and/or over-the-counter drug (e.g., aspirin, ibuprofen, acetaminophen, naproxen)?	 YES  NO	YES

SCHEDULE SESSION 2 _____; Time: _____

REMINDER: If you consume alcohol or use pain medications or pain-relieving creams on the testing area in the 24 hours prior to your session, we will need to reschedule your session. We will email or call you the day before your appointment. Please contact me if you have any questions between now and your appointment

Session 2

All eligibility criteria will also be reviewed with an LHP to confirm there are no changes.

CRITERIA	ANSWER	RESCHEDULE IF
Drug test (tox screen)	 POS  NEG	POS
Pregnancy test (those able to become pregnant)	 POS  NEG	EXCLUDE
In the last 24 hours, have you consumed alcohol?	 YES  NO	YES
Is the participant showing behavioral signs of intoxication? 
 • Speech: overly talkative, argumentative, opinionated or interrupting; stumbling over words; loud, inappropriate language or jokes • Coordination: slowed or delayed reactions, stagger, swagger, or sway • Appearance: vacant or blank expression, smell of alcohol on breath, untidy appearance • Behavior: overly friendly or withdrawn, inappropriate or risky actions, attention difficulties 	 YES  NO	YES
Is the participant showing signs of alcohol withdrawal syndrome (e.g. symptoms of hand tremors, irregular heart rate, fever, nausea, sweating, dehydration, headache, or confusion)?	 YES  NO	YES
In the last 24 hours, have you used a topical pain-relieving cream (e.g. methylsalicylate, capsaicin) on your arms?	 YES  NO	YES
In the last 3 days, have you used any non-steroidal anti-inflammatory drug (NSAID) and/or over-the-counter drug (e.g., aspirin, ibuprofen, acetaminophen, naproxen, sumatriptan)?	 YES  NO	YES

If any of the questions regarding behavioural signs of intoxication or signs of alcohol withdrawal are answered **YES** the subject should be immediately excluded and not rescheduled.

[figure not shown]
[figure not shown]
[figure not shown]
[figure not shown]
[figure not shown]
If one or more other question answers are **YES**:

Is this the first or second time the participant will be rescheduled? (circle one)

[figure not shown]
Rescheduled Appointment:

Date (mm/dd/yyyy): _____ / _____ / _____ Time: _____ AM/PM

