10. Participant has metal in his/her body which would make having an MRI scan unsafe, such as pacemakers, medication pumps, aneurysm clips, metallic prostheses (including metal pins and rods, heart valves or cochlear implants), shrapnel fragments, permanent eye liner or small metal fragments in the eye that welders and other metal workers may have.
11. Participant is uncomfortable in small closed spaces (has claustrophobia) so that he/she would feel uncomfortable in the MRI machine or cannot lie comfortably flat on his/her back for up to 75 minutes in the MRI scanner.
12. Participants weighs more than 550 lbs.
13. Participant has taken any pain medication other than an over-the-counter NSAIDs or acetaminophen within the last month or for more than one month on a continual basis within last six months.
14. Previous participation in 13-AT-0143 (related study).
15. NIH employees who are subordinates, relatives, or co-workers of the investigators, or NCCIH DIR employees.
16. Participants using medications that play into opioid pathways (e.g. loperamide or dextromethorphan), that could potentially interact with naloxone (naltrexone, methylnaltrexone, droperidol, fenfluramine and clonidine)

17. Participant using any herbal supplements (such as yohimbine) due to risk of unknown dangerous interaction as there is no data for herbal preparations and naloxone.
18. Participant has allergies to naloxone or similar drugs.

Exclusion criteria for individual study session

1. Has consumed alcohol within 24 hours, shows signs of alcohol withdrawal syndrome, or has behavioral signs of intoxication will be excluded immediately and not have the possibility to reschedule their session.
2. Used topical pain-relieving creams in the testing area (e.g. methylsalicylate, capsaicin) within 24 hours of testing or used non-steroidal anti-inflammatory drugs (NSAIDS, e.g. aspirin, ibuprofen), acetaminophen, or naproxen within 3 days of testing. *

* To be determined during the pre-session screening (see Attachment 2: Pre-Session Screening). Participants who cannot refrain from these activities may have their session rescheduled up to two times. If the participant is found non-compliant during the second rescheduled appointment, he or she will be excluded from the study.

An Eligibility Checklist can be found in Attachment 2.

4. Study Design and Methods

a. Study overview

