We anticipate recruiting up to 30 potential participants. Participants may be recruited from a currently active NCCIH Phenotyping protocol (16-AT-0077). Participants may also be recruited from the NIH Clinical Trial recruiting line ([name]). When a potential subject contacts us, he or she will be scheduled for a telephone pre-screening session (described below). Cold-calling will not be used to contact or recruit potential participants. NIH employees will not be directly recruited by or through their supervisors to participate in this study. NCCIH employees cannot participate in this protocol.

Telephone Interview (pre-screening)

Each potential participant will undergo a telephone pre-screening interview of approximately 15 minutes (see Attachment 1 for details). During the telephone interview, the subject will be informed about the general procedures of the study, and inclusion/exclusion criteria will be assessed. If the potential subject does not meet these criteria, the interview will be terminated and screening information will be destroyed. However, if the potential participant agrees, we will retain their contact information to contact them later about other studies in the lab for which they may be eligible (including name, email, and phone number). Potentially eligible subjects will be told that to serve as participants they will be required to undergo a drug screening and, for participants who can become pregnant, a pregnancy test. If the potential subject agrees to continue to participate, they will be scheduled for their first session. Further screening information will be drawn from previous participation in the NCCIH Phenotyping Protocol, 16-AT-0077. Participants will be informed of this.

c. Screening

Screening

Screening for this protocol is done under NCCIH protocol 16-AT-0077 (“Clinical and Scientific Assessment of Pain and Painful Disorders”). Screening will be done within a year of participation in this protocol and data required includes clinical MRI, medical exam, psychological interview, sensory testing and the Edinburgh Handedness Inventory. If deemed eligible, the participant will

provide consent for the current protocol prior to performing any procedures specific to this protocol.

Once enrolled in T-AT-0285, a LHP will review eligibility criteria at the beginning of each session, and confirm that participants are eligible and meet pre-session criteria.

d. Study procedures

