Consent will be obtained before any study procedures will be done. Upon arrival at the Clinical Center, the participant will be assigned a CRIS identification number through the NIH Admissions Office. The consent form will be explained and all questions will be answered before the participant is asked to sign the consent form (see Section 14 for details). Consent may occur during an additional, separate visit from the subsequent two research sessions.

Participants eligible to proceed will be asked to undergo two testing sessions, separated by at least 1 day, in the NIH Clinical Research Center's Functional MRI Facility (FMRIF, Building 10, Room B1D307 or B1D305). Each participant will receive naloxone on one day, and saline on the other, with drug order counterbalanced across subjects. At each visit, a urine sample will be collected from all participants for drug screening. In addition, at each visit, participants who are able to become pregnant will also take a urine pregnancy test. Date of onset for previous menstrual cycle will be documented to allow for later analysis of confounds of menstrual cycle in perceptual outcomes. Medical inclusion and exclusion criteria will be reviewed with the participant at the beginning of each study session to confirm continued eligibility. The participants will have their intravenous line placed before any part of the fMRI will start. A baseline scan including data collection for all sensory conditions will be collected before the intravenous infusion. Drug infusion will then start with a bolus injection followed by a continuous infusion of naloxone or saline and the full sensory paradigm will be repeated. An anatomical MRI will also be acquired.

Sensory testing paradigm

Sensory testing will occur on the participant's left lower leg. While it is most common for brushing paradigms to brush on the hairy skin on the arm (C-LTMR fibers primarily innervate

hairy skin), several studies have reported the same preference for slow, C-LTMR brushing on the leg [35], including the shin [36]. According to our unpublished data the calf is also a site of high pleasantness ratings for deep compression, and more accessible in the MRI scanner. We will therefore conduct all sensory testing on subjects' lower leg. Participants will be asked to wear shorts or change into scrubs for each session in order to access the lower leg.

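### Both session-day forms ask about analgesic cream on the arms although only the lower leg is tested, and the documents conflict on whom to exclude and whom to reschedule

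*Combined protocol and SAP*

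**What the plan says.** **Test site.** Section 4d (Sensory testing paradigm) is explicit: "Sensory testing will occur on the participant's left lower leg". The study overview in Section 4a also names the calf.

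**Cream criterion.** Section 3c, criteria for an individual session, item 2, applies to a person who "Used topical pain-relieving creams in the testing area" within 24 hours. A footnote says this is to be settled at pre-session screening and allows up to two reschedulings.

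**Cream question.** The Session 1 and Session 2 forms in Attachment 1 carry the same sentence: "In the last 24 hours, have you used a topical pain-relieving cream (e.g. methylsalicylate, capsaicin) on your arms".

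**Alcohol, intoxication, withdrawal.** Section 3c, session item 1, excludes at once, with no rescheduling, for alcohol within 24 hours and for signs of intoxication or withdrawal. The preamble to the Session 1 form reschedules any yes answer up to twice and excepts only a positive pregnancy test. The Session 2 form lists all three in a column headed for rescheduling. A note after its table then excludes for intoxication or withdrawal signs and sends any other yes to rescheduling.

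**Drug screen.** The telephone script says that a person who tests positive will not be included. The Session 2 form puts a positive result in the rescheduling column.

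**Reminder.** The sentence read to participants before each session gives 24 hours for pain medication. Section 3c and both forms give 3 days for NSAIDs and acetaminophen.

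**The concern.** The session form is the tool the protocol relies on to apply the cream criterion, and it asks about a site where nothing is tested. Taken literally, the row errs both ways: it misses cream on the leg and flags cream on the arms. Methylsalicylate and capsaicin, the form's own examples, are named in a study whose outcomes are ratings of touch and heat on that skin.

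The outcome conflicts matter differently. None of them allows testing that day. They decide whether someone whom one page excludes for good may return, be infused and be analysed. With 24 completers planned and at most 30 enrolled, and with every participant passing this screen twice, eligibility should not depend on which page staff have open. Whichever rule was intended, staff who follow the other page create a protocol deviation.

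**Working it through.** No sample size, power or error rate is involved. The check sets the passages side by side.

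**1. Site.**

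| Source | Site named |
|---|---|
| Section 4d, Sensory testing paradigm | left lower leg |
| Section 3c, session item 2 | testing area |
| Reminders before Sessions 1 and 2 | testing area |
| Session 1 form, cream row | arms |
| Session 2 form, cream row | arms |

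The wrong site appears in 2 of 2 forms. The criterion and both reminders are right, so the error is confined to the forms.

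**2. Do other checks catch cream on the leg?**

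- The next row of both forms asks "have you used any non-steroidal anti-inflammatory drug (NSAID) and/or over-the-counter drug" in the last 3 days. Read literally, this covers an over-the-counter cream. It gives no topical example, follows a separate row about creams, and does not reach a prescription cream that is not an NSAID.
- Section 3c, overall item 13: "Participant has taken any pain medication other than an over-the-counter NSAIDs or acetaminophen within the last month". This helps only if taking a medication includes applying one to the skin.
- The telephone interview asks about medication "in the last 30 days other than over-the-counter NSAIDs or acetaminophen, including OTC, RX, topical pain-relieving creams". It does name creams, but it is not asked on the session day.
- Section 4c has a licensed practitioner "confirm that participants are eligible and meet pre-session criteria" at each session, and Section 4d adds: "Medical inclusion and exclusion criteria will be reviewed with the participant at the beginning of each study session to confirm continued eligibility". These apply the correct criterion, but neither sets down a question about cream on the leg.

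**3. Outcomes** (E = excluded, no return; R = rescheduled; ? = unclear; – = not addressed).

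| Condition | Section 3c | Telephone script | Reminder | Session 1 form | Session 2 column | Note after Session 2 table |
|---|---|---|---|---|---|---|
| Alcohol within 24 h | E | – | R | R (preamble) | R | R (other yes answers) |
| Positive drug screen | no session rule | E | – | ? | R | – |
| Intoxication signs | E | – | – | R (preamble) | R | E |
| Withdrawal signs | E | – | – | R (preamble) | R | E |

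- *Alcohol.* The two-reschedule footnote in Section 3c is attached to item 2, not to item 1, so it does not resolve the conflict. Nor does the note after the Session 2 table, even if it serves both forms, because it sends alcohol to rescheduling.
- *Drug screen.* In the Session 2 column the pregnancy row is marked for exclusion and the drug row is not, so the form marks an exception where it intends one. The Session 1 heading names both actions, and its preamble speaks of yes answers whereas the drug test is scored positive or negative. That entry is therefore left as unclear.
- *Intoxication and withdrawal.* For Session 2 the note overrides the column and agrees with Section 3c. For Session 1 there is a full conflict only if the note does not apply there. If it does, this is a general preamble with a specific override.

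Count: 4 conditions, of which 2 conflict on any layout and 2 depend on it.

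**4. Reminder.** 3 × 24 h = 72 h, and 72 h − 24 h = 48 h. A participant who takes an NSAID in that 48-hour interval has followed the reminder and still fails the form.

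**5. Effect on the estimate.** The primary outcome (Section 9a) is post-drug minus pre-drug, with a baseline in the same session (Section 4d). If cream adds a constant *c* to a rating, then (post + *c*) − (pre + *c*) = post − pre, and *c* cancels. If the cream effect changes during the session, *c*(post) − *c*(pre) remains. The documents give no figure for this or for how often cream is used.

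**The case against.** The strongest reply is that this is one wrong word in a form whose governing criterion is correct. A licensed practitioner confirms the session criteria at every visit, and the forms themselves say so. The telephone question also uses the word taken for creams, which supports reading overall item 13 the same way; prescription creams would then be covered there and over-the-counter ones by the next row of the form. That narrows the gap and is accepted. It does not close it. Item 2 has its own 24-hour window for creams, which suggests they were not meant to fall under item 13, and the practitioner is given no written question about the leg.

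On intoxication and withdrawal signs, the rescheduling block appears once, after Session 2, so the note may well be a shared footer. That is a fair reading, and these two conditions are not counted as firm conflicts.

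On the drug screen, the Session 2 table is irregular and too much may be read into a column heading. Overall item 3 also excludes recreational drug use in the past month, and the second session is due within about 14 days of the first. A failed Session 2 falls on day 1 at the earliest, so a return visit inside that window is at most 13 days later. Taking a month as 30 days, drug use up to 30 − 13 = 17 days before the failed visit would still exclude at the return. This sharpens the conflict: the form offers a return visit that the overall criterion would often bar.

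It is also true that no effect on the trial result has been shown and that the reminder causes only avoidable rescheduling. Both limit the weight of the point; neither makes the passages agree.

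**Conclusion.** The concern holds. Both session forms name a site that is not tested, so detection of cream on the tested leg rests on indirect checks. Alcohol within 24 hours and a positive drug screen have contradictory stated outcomes on any reading of the layout. Intoxication and withdrawal signs do so only if the note after the Session 2 table is confined to Session 2. The reminder's 48-hour gap is a lesser point.

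The likely bias from cream is limited by the same-session baseline, assuming a roughly constant effect within a session; any remainder cannot be estimated from the documents. The outcome conflicts affect who may return and be analysed, not whether an exposed person is tested that day. These are clear errors in operative forms and should be corrected, but they do not undermine the design.

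**What to change.** 1. In both session forms, replace the reference to the arms with the testing area, specified as the lower leg, to match Sections 3c and 4d.
2. Reconcile Section 3c (overall and session criteria), the telephone script, the reminders and both session forms so that alcohol within 24 hours, a positive drug screen, intoxication signs and withdrawal signs each have one stated outcome everywhere. The sponsor should decide which outcome applies.
3. State whether the note after the Session 2 table also covers Session 1, and replace the mixed Session 1 column heading with one outcome per row.
4. Reconcile the reminder's pain-medication window with the 3-day window in Section 3c and the forms.

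The cost is a wording amendment to the forms, reminder and script, plus whichever Section 3c text the sponsor changes. No procedure, visit or staff time is added.
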